10.0 Adverse Events and Participant Withdrawals

The Investigator(s) will be required to provide appropriate information concerning any findings that suggest significant hazards, contraindications, adverse events, or precautions pertinent to the safety of the drug under investigation. Details of pre-existing conditions and adverse events reporting are described below.

Definition of Pre-existing Condition

A pre-existing condition is any chronic or acute sign, symptom, illness, or condition that the participant has at the time of entering the clinical trial; with the exception of those associated with the disease under study.

Definition of Adverse Events (AEs)

An adverse event is any unfavorable and unintended sign, symptom, or disease temporarily associated with the use of a medicinal product, whether or not considered related to the medicinal product.²⁴ The term “adverse event” could include, but not be limited to, any of the following events, which develop or increase in severity during the course of the study:

- Any signs or symptoms whether thought to be related or unrelated to the condition under study
- Any clinically significant laboratory abnormality
- Any abnormality detected during physical examination

The following data will be recorded on the appropriate case report forms (CRFs), regardless of whether they are thought to be associated with the study or the drug under investigation. (“Associated with the use of the drug” means that there is a reasonable possibility that the event may have been caused by the drug.)

- Any event reported by the participant, other than those expected and described in the treatment brochure, will be immediately reported to the treating urologist.
- Signs and symptoms will be graded by the Research Coordinator as mild, moderate, or severe as referenced by Common Toxicity Criteria (CTC) Standard (to be provided with the Manual of Procedures).

Adverse events will be addressed at each participant visit and as reported by the participant, a detailed description of the adverse event will be recorded on the Adverse Event CRF. Adverse Event CRFs will be reviewed regularly by the DCC and reports will be produced on a quarterly basis summarizing the adverse events by clinical center and masked treatment assignment.

All adverse events (clinical signs, laboratory values or other) must be followed until the return to normal or until stabilization of the patient conditions.

10.1 Serious Adverse Events

Definition of Serious Adverse Events (SAEs)

A serious adverse event is defined as any untoward (unwanted) medical occurrence that at ANY dose

- Results in death
- Is life-threatening
- Results in a persistent or significant disability/incapacity
- Results in in-patient hospitalization or prolongation of existing hospitalization
- Results in a congenital anomaly/birth defect

Important medical events that may not result in death, be life threatening, or require hospitalization may be considered a serious adverse drug experience when, based upon medical judgment, they may jeopardize the patient or participant and may require medical or surgical intervention to prevent one of the outcomes listed in this definition.²⁵ Examples of such medical events include allergic bronchospasm requiring intensive treatment in an emergency room or at home, blood dyscrasias or convulsions that do not result in inpatient hospitalization, or development of drug dependency or drug abuse.

10.2 Reporting Obligations for SAEs and IND Safety Reports

The Clinical Site is responsible for reporting SAEs to the DCC within 24 hours of first knowledge of the event via telephone, followed by a facsimile (which includes both the corresponding Adverse Event Case Report Form and the MedWatch Form). In addition, the site must promptly report all SAEs to their IRB via written/dated notification in accordance to the IRB's reporting requirements. Copies of all such correspondence must be maintained in the clinical site's main study binder.

Upon notification from the clinical site, the DCC will notify the sponsor (NIDDK) of SAEs within one (1) working day. Should any SAEs fall into the category of IND Safety Reports (serious, unexpected, and possibly related to drug), the DCC will work with the NIDDK to report the event to the FDA and all investigational sites in accordance to the process and timelines specified in the FDA regulations. DCC will serve as the sponsor's designee by disseminating the IND safety reports to all clinical sites and promptly notifying the Licensed Product Holders. All DSMB members will also be apprised of all SAEs following the timelines above.

10.3 Follow-Up of Serious Adverse Events

All serious adverse events must be followed with appropriate medical management until resolved or until progression has been stabilized.

10.4 Unmasking (Unblinding) of Treatment

At the end of Visit #2, participants will be randomly assigned to one of the two treatment groups following a randomization schedule generated by the DCC prior to study initiation. Neither the Principal Investigator nor the investigational site personnel will know the treatment group to which any participant is randomized. If there is a serious adverse event which is thought by the clinical site staff to be possibly or probably related to the coded medication, the clinical site staff, when necessary for the safety of the participant, will unmask treatment group assignment upon conferring with the clinical site Principal Investigator. The clinical site staff must report the unmasking to the DCC within one (1) working day, to be followed by submission of a detailed report to the DCC within three (3) working days of the initial DCC contact. The clinical site must also promptly notify their IRB of the unmasking occurrence in accordance to reporting requirements.

In accordance to the ICH *Guideline for Industry Clinical Safety Data Management's* section on expedited reporting: "Although it is advantageous to retain the blind for all patients prior to final study analysis, when a serious adverse event is judged reportable on an expedited basis, it is recommended that the blind be broken only for that specific patient by the sponsor even if the investigator has not broken the blind. It is also recommended that, when possible and appropriate, the blind be maintained for those persons, such as biometrics personnel, responsible for analysis and interpretation of results at the study's conclusion." For the purposes of this protocol, if dissemination of this unmasking information from the Sponsor to the Licensed Product Holders is requested, a collaborative discussion regarding the appropriate process will be initiated.

Unmasking of treatment assignment is anticipated to be an uncommon occurrence and is highly discouraged. At the end of the trial, each participant will be asked to which treatment arm s/he thought s/he had been assigned to aid in evaluating the success of the blinding.

10.5 Participant Withdrawals

It is expected that some participants may drop out of the trial due to side effects or lack of efficacy prior to the six (6) week endpoint. However, all attempts will be made to get complete data on all participants, including those who cease treatment prior to six (6) weeks, in order to conduct the primary intent-to-treat analysis for secondary endpoints. It is expected that a maximum of 15% of participants will withdraw completely from treatment AND follow-up prior to six (6) weeks.

Under certain circumstances, a study participant may have his treatment terminated prior to the six (6) week clinic visit. These circumstances include: unacceptable concomitant medications/treatments, unacceptable adverse events as determined by the Principal Investigator (PI), participant dissatisfaction with treatment, or participant disinterest in continued study participation. In addition, any participant who acquires a serious or life-threatening medical condition while participating in the study may have the study treatment terminated early at the discretion of the PI. A participant may also undergo early study termination because of a change of residence outside the driving distance of the CPCRN-2 network.

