5.0 Study Endpoints

5.1 Primary Endpoint

The primary endpoint to be used for efficacy evaluation is the response rate, defined as a 6-point decrease from baseline to 6 weeks in the NIH-CPSI Total Score (scale of 0 - 43).¹⁸ The decision to use this 6-point cut-off is based on analysis of the previous CPCRn clinical trial on ciprofloxacin and tamsulosin.¹⁹ The NIH-CPSI total score responsiveness to change, from baseline to 6-weeks, was examined relative to the GRA outcome scale and the two scales were shown to have a high correlation. Among those who reported “moderately improved” or “markedly improved” (n=39) on the GRA, 30 participants reported a ≥ 6 -point decrease. This translates into 77% sensitivity and 71% specificity.

The responder criteria based on a 6-point decrease in the CPSI Total Score will allow detection of clinically detectable improvement in symptoms, as the goal is to identify treatment agents with solid clinical efficacy.

Using a 6-point decrease rather than the mean score change as primary outcome may result in somewhat less statistical power, but it allows study withdrawals to be considered as non-responders for an intent-to-treat analysis. (The dropout rate for the previous CPCRn trial was approximately 10% over 6-12 weeks).

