9.4 Telephone contacts

Telephone Contact #1 (Visit #3)- The research coordinator will contact the participant after completion of the 150mg dose in order to determine adverse effects of medication and to monitor tolerance. The research coordinator will also administer the NIH-CPSI and SYM questionnaires (including the GRA question) over the phone.

Telephone Contact #2 (Visit #4)- The research coordinator will contact the participant after completion of the 300mg dose in order to determine adverse effects of medication and to monitor tolerance. The research coordinator will also administer the NIH-CPSI and SYM questionnaires (including the GRA question) over the phone.

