9.5 Treatment Visit (Visit #5)

The participant will be required to return for a third clinic visit six weeks after treatment start. The primary efficacy measure is the CPSI.

- *Concomitant Medications.* The research staff will record the medications currently being taken by the participant. Participants will be asked to recall their medications if they fail to bring them to the second screening visit.
- *Adverse Events/Serious Adverse Events.* The research staff will record any adverse events that have newly occurred, changed, or been resolved.

- *Symptom Questionnaires.* As in the Screening/Randomization Visit (Visit #2), the participant will be required to complete a number of different questionnaires, with the addition of the single question GRA.

Unused study medications will be returned and the RC will do a pill count and assess drug compliance. The *Study Stop Form* and *Treatment Stop Form* will also be completed at this visit for those participants not continuing on to Phase II.

At this visit, sites that choose to will have the option of asking whether the participant is willing to provide a second urine and EPS specimen, provided that this additional procedure is specified in the site's informed consent.

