12.4 Intent-to-Treat Analyses and Missing Data

An intent-to-treat analysis, including all randomized participants, will be used for the primary comparison of treatments. All attempts will be made to keep missing data to a minimum. Participants who discontinue treatment during the trial, particularly in the case of an adverse event, will not be considered withdrawals from study unless they withdraw consent for further follow-up. These participants will be encouraged to continue on study in order to provide complete follow-up information. However, it is expected that up to 15% of the randomized participants may withdraw prior to the final assessment of response at six (6)

weeks. These participants will be considered treatment failures and included in the denominator for evaluation of response rates defined for the primary endpoint.

The characteristics at time of randomization for those participants without complete follow-up will be examined; however, there will be limited statistical power to detect any but major differences between these participants and those with complete follow-up. In addition, in order to assess the potential biases introduced by differential withdrawal among treatment arms, a comparison of withdrawal rates and/or time to withdrawal will be included as an ancillary analysis to the primary endpoint comparison.

In general, missing data will not be imputed. The possible exception is validated symptom scales for which methods of imputing missing items have been previously developed. For example, the following procedure will be used to calculate the NIH-CPSI Pain Score in the event there are missing responses. If no more than two binary items are missing from the NIH-CPSI questions 1a-1d, 2a, 2b, and no other pain items are missing, the NIH-CPSI Pain Score will be imputed as follows: $\text{sum of all non-missing items} * 21 / (21 - \# \text{ missing items})$. If only question #3 is missing then the NIH-CPSI pain score will be imputed as follows: $\text{sum of all non-missing items} * (21/16)$. Every effort will be made to use statistical methods that are robust to missingness, and the number of subjects included with each analysis will be given with the results.

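### A move outside the network can end a man's study participation and make him a non-responder, and no telephone route to the week-6 NIH-CPSI is stated, although the telephone is used at other visits

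*Combined protocol and SAP*

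**What the plan says.** - **Section 10.5** lists reasons for ending treatment early and then adds a reason for ending study participation: "A participant may also undergo early study termination because of a change of residence outside the driving distance of the CPCRN-2 network". Earlier in the same section the aim is that "all attempts will be made to get complete data on all participants", and men who have stopped treatment are expressly included.
- **Section 12.4** says that participants who discontinue treatment "will not be considered withdrawals from study unless they withdraw consent for further follow-up". Of those who withdraw before the week-6 assessment it says: "These participants will be considered treatment failures and included in the denominator for evaluation of response rates defined for the primary endpoint". It adds: "In general, missing data will not be imputed".
- **Section 5.1** gives as a reason for the responder endpoint that "it allows study withdrawals to be considered as non-responders for an intent-to-treat analysis". Section 12.7 repeats this.
- **Section 9.5**, on the primary time point: "The participant will be required to return for a third clinic visit six weeks after treatment start". It states no other way to collect the week-6 score.
- **Section 9.4**, on weeks 2 and 4: "The research coordinator will also administer the NIH-CPSI and SYM questionnaires (including the GRA question) over the phone". Section 9.6 and Appendix A also have the NIH-CPSI completed at the week-7 telephone contact (Visit 6), and Section 9.7 uses the telephone again in Phase II.
- **Appendix A** lists a Participant Transfer form, used as needed.

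**The concern.** A man who moves away in the six weeks after randomization may be quite willing to answer the questionnaire. Under Section 10.5 a site may nevertheless close his participation. His outcome is then a failure because of his address, not because of his symptoms. The instrument that would give his real outcome is one the coordinator already reads to him by telephone.

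The clause also exposes a second, separate gap. No remote route to the week-6 score is stated for any man who does not come to Visit 5, including one who has stopped the drug and whom the plan wants to keep in follow-up.

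At stake is avoidable misclassification on the primary endpoint. Responders wrongly scored as failures pull both response rates down and shrink the difference between them.

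**Working it through.** **Step 1. How a terminated man is scored.** Section 12.4 speaks of men who withdraw; Section 10.5 speaks of termination. Failure scoring of a terminated man is therefore an inference, but a short one. The clause stands under the heading on participant withdrawals, the primary analysis includes every randomized man, missing scores are in general not imputed, and without a week-6 score no 6-point fall can be shown.

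**Step 2. Inputs.** From Section 12.2: placebo 40%, pregabalin 60%, two-sided alpha 0.05, power 90%, allocation 2:1, total 287 unadjusted and 318 adjusted (212 and 106). The adjustments named are one interim analysis and 10% for center variation; none is named for withdrawal. The share r of men lost through relocation is not in the documents. It is an assumption here, taken as equal in both arms and unrelated to outcome.

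**Step 3. Reproduce the plan's sample size** (normal approximation, pooled variance under the null, no continuity correction).

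Pooled rate = (0.40 + 2 × 0.60)/3 = 0.5333.

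n(placebo) = [1.960 × √(1.5 × 0.5333 × 0.4667) + 1.282 × √(0.40 × 0.60 + 0.60 × 0.40/2)]² / 0.20² = 96.7, rounded up to 97.

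Total = 3 × 97 = 291, against 287 stated. With unpooled variance the total is 284. Then 287 × 1.10 = 315.7, against 318 stated; the interim adjustment and rounding can account for the rest. The plan's figures reproduce to within 3%, and this point disputes none of them.

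**Step 4. Effect of scoring a share r as failures.** The rates become 0.60(1 − r) and 0.40(1 − r), so the difference is 0.20(1 − r): each 1% costs 0.2 percentage points.

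Power = Φ[(difference − 1.960 × SE0)/SE1], where SE0 uses the pooled rate and SE1 the separate rates. At r = 0 with 212 and 106 men, SE0 = 0.05935 and SE1 = 0.05828, so power = Φ(1.436) = 92.4%.

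| r (assumed) | Men of 318 | Rates | Difference | Power, 212/106 | Power, effective total 289 |
|---|---|---|---|---|---|
| 0% | 0 | 60.0% / 40.0% | 20.0 | 92.4% | 89.9% |
| 1% | about 3 | 59.4% / 39.6% | 19.8 | 91.9% | 89.3% |
| 2% | about 6 | 58.8% / 39.2% | 19.6 | 91.4% | 88.7% |
| 3% | about 10 | 58.2% / 38.8% | 19.4 | 90.8% | 88.0% |
| 5% | about 16 | 57.0% / 38.0% | 19.0 | 89.7% | 86.7% |

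The last column treats the 10% center inflation as already used up (318/1.10 = 289). In either column each 1% lost costs about 0.5 to 0.6 points of power. The r = 0 row is also what full telephone recovery of these men would give.

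**The case against.** The strongest reply is that the clause is narrow. Termination is optional, it needs a move beyond driving distance of the whole network, only a six-week window matters, and the transfer form covers a move to another site. Counting withdrawals as non-responders is a deliberate choice whose power cost Sections 5.1 and 12.7 acknowledge, and Section 12.4 plans a comparison of withdrawal between arms. Nothing forbids a telephone call at week 6, and details may sit in the Manual of Procedures or the Data Analysis and Monitoring Plan, which are not available here. A telephone fallback also has a price: baseline scores are collected in clinic, and the documents do not show that the two modes give equal scores.

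Most of this stands, and it limits the point in four ways. A reader might infer more than the documents support:

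- **That only withdrawal of consent counts as leaving the study.** The sentence in Section 12.4 is about men who discontinue treatment. It is not a general rule, so the clash with Section 10.5 is one of principle more than a flat contradiction.
- **That men who stop the drug and will not travel may be terminated.** Section 10.5 says the opposite in intent. For them only the mode of collection is unstated.
- **That the expected 15% withdrawal measures this loss.** That figure is an all-cause maximum for men leaving both treatment and follow-up, and many of them would not take a call.
- **That relocation biases the comparison.** Nothing links moving house to treatment arm. Loss among men who stop for side effects could differ by arm, but the documents give no figures from which to size that, and it is not what the relocation clause governs.

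What the reply does not remove is that following Section 10.5 as written can discard a primary outcome that the trial's own telephone procedure could obtain.

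**Conclusion.** The point holds in a limited form. The relocation clause in Section 10.5 sits badly with the aim of complete data in the same section and with the follow-up principle in Section 12.4. Separately, Section 9.5 leaves week 6 without a stated telephone route.

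The size is small. If relocation removes 1% to 3% of men, power with 212 and 106 stays above 90%; it reaches 89.7% only at 5%. These figures assume true rates of 60% and 40%, equal loss in both arms, and loss unrelated to outcome. The relocation rate itself is unknown. The documents also do not say whether the 60% and 40% already count withdrawals as failures; if they do, part of this loss is already in the design. The change is worth making because it protects the primary endpoint at little cost, not because the trial is at risk without it.

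**What to change.** 1. **Section 10.5:** state that a change of residence may end clinic attendance but does not end follow-up, and reconcile the wording with Section 12.4. How study treatment is handled after a move is a separate matter, on which nothing is proposed here.
2. **Sections 9.5 and 12.4:** state that when Visit 5 cannot be attended, by a man on or off treatment, the week-6 NIH-CPSI and GRA are given by telephone under the Section 9.4 procedure, and that this NIH-CPSI score is used for the primary endpoint. Record the mode. Score as failures only men with no week-6 NIH-CPSI by either route.
3. **Sensitivity analysis:** repeat the primary comparison with every man whose only week-6 score came by telephone kept in the denominator and counted as a non-responder. This shows the result with no telephone score used.

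The cost is protocol wording and one mode field on a form, using existing staff and an existing procedure. The downside is that a few week-6 scores will come by telephone against a clinic baseline, and the share could differ somewhat by arm. For that reason the mode should be recorded and tabulated by arm.

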11.0 Administrative Responsibilities

11.1 General Considerations and the Manual of Operating Procedures (MOP)

The DCC has developed written standard operating procedures (SOPs) to ensure that all aspects of the randomized clinical trial are conducted in a standard and uniform manner. These procedures will be organized into a Manual of Procedures (MOP), which will comply with the protocol, GCP, and applicable regulatory requirements. All study-associated personnel will be trained in study conduct and procedures prior to the start of the trial. A data and safety monitoring plan and data-monitoring schedule will be developed to assess protocol adherence. This plan will be presented to the DSMB for approval for implementation.

11.2 Institutional Review Board

It is the responsibility of the Principal Investigator at each site to provide the appropriate Institutional Review Board (IRB) with all pertinent material, including a copy of the informed consent. Approval of the protocol and the informed consent form must be obtained and forwarded to the sponsor prior to screening or enrolling any subjects. The Investigator also maintains the responsibility of initiating protocol re-approval, notification of protocol and/or consent form changes, notification of adverse reactions, and termination of the study according to the appropriate IRB requirements.

